3.1.1 Target lesions (TLs)

Measurable disease is defined as having at least one measurable lesion, not previously irradiated, which is ≥ 10 mm in the longest diameter (LD) (except lymph nodes which must have short axis ≥ 15 mm) with computed tomography (CT) or magnetic resonance imaging (MRI) and which is suitable for accurate repeated measurements. A patient can have a maximum of 5 measurable lesions recorded at baseline with a maximum of 2 lesions per organ (representative of all lesions involved suitable for accurate repeated measurement) and these are referred to as target lesions (TLs). If more than one baseline scan is recorded then measurements from the one that is closest and prior to start of treatment will be used to define the baseline sum of TLs. It may be the case that, on occasion, the largest lesion does not lend itself to reproducible measurement in which circumstance the next largest lesion, which can be measured reproducibly, should be selected. All other lesions (or sites of disease) not recorded as TL should be identified as NTL at baseline. Measurements are not required for these lesions, but their status should be followed at subsequent visits.

Table 3 TL visit responses

Visit Responses	Description
Complete Response (CR)	Disappearance of all TLs. Any pathological lymph nodes selected as TLs must have a reduction in short axis to <10mm.
Partial response (PR)	At least a 30% decrease in the sum of diameters of TLs, taking as reference the baseline sum of diameters as long as criteria for PD are not met.
Progressive disease (PD)	A $\geq 20\%$ increase in the sum of diameters of TLs and an absolute increase of ≥ 5 mm, taking as reference the smallest sum of diameters since treatment started including the baseline sum of diameters.
Stable disease (SD)	Neither sufficient shrinkage to qualify for PR nor sufficient increase to qualify for PD. Stable disease can only be declared at or after the first scheduled RECIST scan.
Not Evaluable (NE)	Only relevant in certain situations (i.e. if any of the target lesions were not assessed or not evaluable or had a lesion intervention at this visit; and scaling up could not be performed for lesions with interventions). Note: If the sum of diameters meets the progressive disease criteria, progressive disease overrides not evaluable as a target lesion response

Rounding of TL data

For calculation of PD and PR for TLs percentage changes from baseline and previous minimum should be rounded to 1 d.p. before assigning a TL response. For example 19.95% should be rounded to 20.0% but 19.94% should be rounded to 19.9%

Missing TL data

For a visit to be evaluable then all TL measurements should be recorded. However, a visit response of PD should still be assigned if any of the following occurred

- A new lesion is recorded
- A NTL visit response of PD is recorded
- The sum of TLs is sufficiently increased to result in a 20% increase, and an absolute increase of ≥ 5 mm, from nadir even assuming the non-recorded TLs have disappeared

Note: the nadir can only be taken from assessments where all the TLs had a LD recorded.

If there is at least one TL measurement missing and a visit response of PD cannot be assigned, the visit response is not evaluable (NE).

Lymph nodes

For lymph nodes, if the size reduces to < 10 mm then these are considered non-pathological. However a size will still be given and this size should still be used to determine the TL visit response as normal. In the special case where all lymph nodes are < 10 mm and all other TLs are 0mm then although the sum may be >0 mm the calculation of TL response should be over-written as a CR.

TL visit responses subsequent to CR

A CR can only be followed by CR, PD or NE. If a CR has occurred then the following rules at the subsequent visits must be applied:

- Step 1: If all lesions meet the CR criteria (i.e. 0mm or < 10 mm for lymph nodes) then response will be set to CR irrespective of whether the criteria for PD of TL is also met i.e. if a lymph node LD increases by 20% but remains < 10 mm.
- Step 2: If some lesion measurements are missing but all other lesions meet the CR criteria (i.e. 0mm or < 10 mm for lymph nodes) then response will be set to NE irrespective of whether, when referencing the sum of TL diameters, the criteria for PD are also met.
- Step 3: If not all lesions meet the CR criteria and the sum of lesions meets the criteria for PD then response will be set to PD
- Step 4: If after steps 1 – 3 a response can still not be determined the response will be set to remain as CR

TL too big to measure

If a TL becomes too big to measure this should be indicated in the database and a size ('x') above which it cannot be accurately measured should be recorded. If using a value of x in the calculation of TL response would not give an overall visit response of PD, then this will be flagged and reviewed by the study team blinded to treatment assignment. It is expected that a visit response of PD will remain in the vast majority of cases.

TL too small to measure

If a TL becomes too small to measure a value of 5mm will be entered into the database and used in TL calculations, unless the radiologist has indicated and entered a smaller value that can be reliably measured. If a TL response of PD results then this will be reviewed by the study team blinded to treatment assignment.

Irradiated lesions/lesion intervention

Previously irradiated lesions (i.e. lesion irradiated prior to entry into the study) should be recorded as NTLs and should not form part of the TL assessment.

Any TL (including lymph nodes), which has had intervention during the study (for example, irradiation / palliative surgery / embolisation), should be handled in the following way and once a lesion has had intervention then it should be treated as having intervention for the remainder of the study noting that an intervention will most likely shrink the size of tumors:

- Step 1: the diameters of the TLs (including the lesions that have had intervention) will be summed and the calculation will be performed in the usual manner. If the visit response is PD this will remain as a valid response category.
- Step 2: If there was no evidence of progression after step 1, ignore the lesion diameter for those lesions with intervention and scale up as described below as long as there remain $\leq 1/3$ of the TLs with intervention. If the scaling results in a visit response of PD then the patient would be assigned a TL response of PD.
- Step 3: If after both steps PD has not been assigned, then, if appropriate, a scaled sum of diameters will be calculated (as long as $\leq 1/3$ of the TLs have interventions), and PR or SD then assigned as the visit response. Patients with intervention are evaluable for CR as long as all non-intervened lesions are 0 (or $<10\text{mm}$ for lymph nodes) and each lesion that has experienced intervention also has a value of 0 recorded. If scaling up is not appropriate due to too few lesions without intervention then the visit response will be set as NE.

At subsequent visits the above steps will be repeated to determine the TL and overall visit response. When calculating the previous minimum sum of TL diameters, lesions with intervention should not be used and the sum of diameters scaled up where appropriate (as per step 2 above).

If $\leq 1/3$ of the TL measurements have interventions then the results will be scaled up based on the sizes at the nadir visit, to give an estimated sum of diameters and this will be used in calculations; this is equivalent to comparing the visit sum of diameters of the non-intervention lesions to the nadir sum of diameters excluding the lesions with interventions..

If $> 1/3$ of TL measurements have interventions then TL response will be NE, unless the sum of diameters of TL without intervention would result in PD (i.e. if using a value of 0 for non-intervention lesions, the sum of diameters has still increased by 20% or more compared to nadir and the sum of TLs has increased by ≥ 5 mm from nadir).

Example of scaling

Lesion	Longest diameter at nadir visit	Longest diameter at follow-up visit
1	7.2	7.1
2	6.7	6.4
3	4.3	4.0
4	8.6	8.5
5	2.5	Intervention
Sum	29.3	26

Lesion 5 has had an intervention at the follow-up visit.

The sum of lesions 1-4 at the follow-up is 26 cm. The sum of the corresponding lesions at nadir visit is 26.8 cm.

Scale up as follows to give an estimated TL sum of 28.4cm:

$$\frac{26}{26.8} \times 29.3 = 28.4\text{cm}$$

CR will not be allowed as a TL response for visits where there are lesions with intervention. Only PR, SD or PD (or NE) could be assigned as the TL visit response in these cases. However, for visits with $\leq 1/3$ lesion assessments with intervention, the scaled up sum of TLs diameters will be included when defining the nadir value for the assessment of progression.

Lesions that split in two

If a TL splits in two, then the LDs of the split lesions should be summed and reported as the LD for the lesion that split.

Lesions that merge

If two TLs merge, then the LD of the merged lesion should be recorded for one of the TL sizes and the other TL size should be recorded as 0cm.

Change in method of assessment of TLs

CT, MRI and clinical examination are the only methods of assessment that can be used within a trial, with CT and MRI being the preferred methods and clinical examination only used in special cases. If a change in method of assessment occurs between CT and MRI this will be considered acceptable and no adjustment within the programming is needed.

If a change in method involves clinical examination (e.g. CT changes to clinical examination or vice versa), any affected lesions should be treated as missing.

3.1.2 Non-Target Lesions (NTLs) and new lesions.

At each visit an overall assessment of the NTL response should be recorded by the investigator. This section provides the definitions of the criteria used to determine and record overall response for NTL at the investigational site at each visit.

NTL response will be derived based on the Investigator’s overall assessment of NTLs as follows:

Table 4 NTL Visit Responses

Visit Responses	Description
Complete Response (CR)	Disappearance of all NTLs present at baseline with all lymph nodes non-pathological in size (<10 mm short axis).
Progressive Disease (PD)	Unequivocal progression of existing NTLs. Unequivocal progression may be due to an important progression in one lesion only or in several lesions. In all cases the progression MUST be clinically significant for the physician to consider changing (or stopping) therapy.
Non-CR/Non-PD	Persistence of one or more NTLs with no evidence of progression.
Not Evaluable (NE)	Only relevant when one or some of the NTLs were not assessed and, in the investigator's opinion, they are not able to provide an evaluable overall NTL assessment at this visit. Note: For patients without TLs at baseline, this is relevant if any of the NTLs were not assessed at this visit and the progression criteria have not been met.
Not Applicable (NA)	Only relevant if there are no NTLs at baseline

To achieve ‘unequivocal progression’ on the basis of NTLs, there must be an overall level of substantial worsening in non-target disease such that, even in the presence of SD or PR in TLs, the overall tumor burden has increased sufficiently to merit a determination of disease progression. A modest ‘increase’ in the size of one or more NTLs is usually not sufficient to qualify for unequivocal progression status.

Details of any new lesions will also be recorded with the date of assessment. The presence of one or more new lesions is assessed as progression.

A lesion identified at a follow up assessment in an anatomical location that was not scanned at baseline is considered a new lesion and will indicate disease progression.

The finding of a new lesion should be unequivocal: i.e. not attributable to differences in scanning technique, change in imaging modality or findings thought to represent something other than tumor.

New lesions will be identified via a Yes/No tick box. The absence and presence of new lesions at each visit should be listed alongside the TL and NTL visit responses.

A new lesion indicates progression so the overall visit response will be PD irrespective of the TL and NTL response.

If the question ‘Any new lesions since baseline’ has not been answered with Yes or No and the new lesion details are blank this is not evidence that no new lesions are present, but should not overtly affect the derivation.

Symptomatic progression is not a descriptor for progression of NTLs: it is a reason for stopping study therapy and will not be included in any assessment of NTLs.

Patients with ‘symptomatic progression’ requiring discontinuation of treatment without objective evidence of disease progression at that time should continue to undergo tumor assessments where possible until objective disease progression is observed.

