8.4.1 Primary Endpoint

Objective Response Rate (ORR)

ORR is defined as the number (%) of patients with measurable disease at baseline, with at least one visit response of CR or PR that is confirmed at least 4 weeks later. For the primary analysis ICR is required for both the initial response and confirmation. Data obtained up until progression, or last evaluable assessment in the absence of progression, will be included in the assessment of ORR. However, any CR or PR which occurred or was confirmed after a further anticancer therapy was received will not be included in numerator of the ORR calculation. In the case where a patient has two non-consecutive visit responses of PR or CR, then, as long as the time between the 2 visits of PR or CR is greater than 4 weeks and there is no PD between the PR visits, the patient will be defined as a responder. Note that CR followed by PR is classed as progression.

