CR	SD	Scenario not possible, CR can only be followed by CR PD, NE	SD provided minimum criteria for SD duration met, otherwise, PD
CR	PD	No	SD provided minimum criteria for SD duration met, otherwise, PD
CR	NE	No	SD provided minimum criteria for SD duration met, otherwise NE
PR	CR	Yes	PR
PR	PR	Yes	PR
PR	SD	No	SD
PR	PD	No	SD provided minimum criteria for SD duration met, otherwise, PD
PR	NE	No	SD provided minimum criteria for SD duration met, otherwise NE
CR/PR	Second timepoint not reached at time of analysis	No*	SD provided minimum criteria for SD duration met, otherwise NE
CR/PR	Patient withdrew consent before second timepoint reached	No*	SD provided minimum criteria for SD duration met, otherwise NE
NE	NE		NE

CR = complete response, PR = partial response, SD = stable disease, PD = progressive disease, and NE = inevaluable. (Eisenhauer et al 2009).

* Note for the interim analysis, ORR will include both confirmed and unconfirmed responses, so patients in these scenarios would be counted as responders.

^a If a CR is truly met at first time point, then any disease seen at a subsequent time point, even disease meeting PR criteria relative to baseline, makes the disease PD at that point (since disease must have reappeared after CR). Best response would depend on whether minimum duration for SD was met (scan at least 7 weeks post-baseline). However, sometimes 'CR' may be claimed when subsequent scans suggest small lesions were likely still present and in fact the patient had PR, not CR at the first time point. Under these circumstances, the original CR should be changed to PR and the best response is PR.

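### SAP 3.1.1 Step 4 keeps an investigator target-lesion response at CR when target disease is visible again below the PD threshold, contrary to SAP Table 3, Table 6 footnote a and Protocol 8.4.1

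*SAP*

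**What the plan says.** SAP 3.1.1 (TL visit responses subsequent to CR) starts from the rule "A CR can only be followed by CR, PD or NE". Step 1 keeps CR when every target lesion still meets the CR criteria. Step 2 gives NE when some measurements are missing and the rest meet them. Step 3 reads: "If not all lesions meet the CR criteria and the sum of lesions meets the criteria for PD then response will be set to PD". The last step covers whatever is left: "a response can still not be determined the response will be set to remain as CR".

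Four other places bear on those remaining visits:

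- SAP Table 3 defines target-lesion CR as "Disappearance of all TLs. Any pathological lymph nodes selected as TLs must have a reduction in short axis to <10mm". It defines PD as a rise of at least 20% and at least 5 mm, "taking as reference the smallest sum of diameters since treatment started including the baseline sum of diameters".
- SAP Table 6 footnote a says that after a true CR "any disease seen at a subsequent time point, even disease meeting PR criteria relative to baseline, makes the disease PD at that point". Its alternative, where small lesions were probably present all along, is to change the earlier CR to PR.
- Protocol 8.4.1: "Note that CR followed by PR is classed as progression".
- SAP section 6, which lists changes from the protocol, does not mention the matter.

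**The concern.** Step 4 is worded for visits that cannot be determined. In practice it receives visits where the finding is clear: target disease is present, but its growth is below the PD threshold. The SAP bars PR and SD after a CR, so the algorithm falls back on the most favourable category. That result fails the SAP's own definition of CR, and neither branch of footnote a would give it.

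If non-target disease is CR or not applicable and no new lesion is recorded, Table 5 turns the target-lesion CR into an overall CR. Two CR visits then make a confirmed responder with best response CR in Table 6. The investigator DoR and PFS clocks run past the reappearance.

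**Working it through.** **Inputs.** Steps 1 to 4, the Table 3 PD rule and the missing-data rule come from SAP 3.1.1. The overall response comes from Table 5 and confirmation from Table 6. The limit of two target lesions per organ, lymph nodes included, is in Protocol Appendix F. The planned sample is about 60.

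**Assumption.** The SAP does not define a percentage rise from a sum of 0 mm. I count any rise from 0 mm as at least 20%, so only the 5 mm limit matters there.

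**Which limit binds.** At CR, non-nodal target lesions are 0 mm and at most two target nodes remain, each below 10 mm. The sum is therefore below 20 mm, and 20% of it is below 0.20 × 20 = 4 mm. The 5 mm limit is always the stricter one.

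**Test cases, Table 3 threshold (at least 5 mm).**

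| Change since CR | Sum, mm | Rise | Step | Result |
|---|---|---|---|---|
| Non-nodal 0 to 4 | 0 to 4 | 4 mm | 4 | CR |
| Two non-nodal, 0+0 to 2+2 | 0 to 4 | 4 mm | 4 | CR |
| Node 9 to 13 | 9 to 13 | 4 mm (4/9 = 44.4%) | 4 | CR |
| Node 9 to 4, non-nodal 0 to 9 | 9 to 13 | 4 mm (44.4%) | 4 | CR |
| One lesion missing, another 0 to 4 | not complete | not PD | 4 | CR |
| Non-nodal 0 to 5 | 0 to 5 | 5 mm | 3 | PD |
| Node 9 to 14 | 9 to 14 | 5 mm (5/9 = 55.6%) | 3 | PD |

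The fourth row shows that the rule acts on the sum: a shrinking node can hide a 9 mm regrowth. In the fifth row, the SAP's missing-data rule would give NE.

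The last two rows depend on which threshold is used. The PFS definition in SAP 3.2.2 (and Protocol 8.4.2) requires more than 5 mm. Under that wording both rows also go to Step 4 and return CR.

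**Against the other rules.** A 4 mm lesion with a 10 mm baseline has changed by (4 − 10)/10 = −60%, which is PR relative to baseline. Footnote a and Protocol 8.4.1 call that progression after a CR. Step 4 calls it CR.

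**Size for investigator ORR.** One responder in 60 is 1/60 = 1.7 points; for illustration, 15/60 = 25.0% becomes 14/60 = 23.3%. That loss needs all of the following:

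- CR was the first response seen.
- The Step 4 visit is its only confirmation.
- Non-target response is CR or not applicable, with no new lesion.
- The corrected visit is PD.

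A patient with PR and then CR is already a confirmed responder in Table 6, so ORR does not move. If the earlier CR is changed to PR, footnote a keeps best response at PR, and only the CR/PR split moves.

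**The case against.** The strongest defence is scope. SAP 3.1 has the central reviewers supply their own visit responses, so this algorithm does not touch the primary ORR. SAP section 5 counts unconfirmed responses at the futility look, so a false confirmation changes nothing there. SAP Table 2 labels the investigator analyses as sensitivity analyses, although SAP section 3 also makes investigator ORR a secondary endpoint. All of this stands. A reader might infer that the primary endpoint is inflated; the documents do not support that.

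There are also partial safeguards. A reappearance recorded as a new lesion is PD whatever the target-lesion result. A lesion too small to measure is entered as 5 mm, which meets Table 3's limit from a sum of 0 mm and then goes to study-team review. These narrow the gap without closing it:

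- A smaller value is used when it can be measured reliably.
- Neither document says that a reappearing target lesion counts as new, and the SAP asks about new lesions since baseline.
- A regrown target node was already recorded at baseline.

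Step 4 might be meant to absorb measurement noise. The SAP does not say so, and footnote a already deals with doubtful CRs by changing them to PR. The noise argument does carry weight for nodes. A change from 9 to 10 mm is +11.1% and 1 mm, and calling it PD would conflict with the 20% and 5 mm rule.

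**Conclusion.** The contradiction is real and the correction is minor. As written, Step 4 returns CR for visits that fail Table 3's definition of CR and that footnote a and Protocol 8.4.1 would not leave as CR. It affects investigator BoR, ORR, DoR, DCR and PFS only.

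Cases should be rare, and their number cannot be derived from the documents. The effect on investigator ORR is at most 1.7 points per case at N = 60, under the conditions listed above. Otherwise only the CR/PR split or a DoR/PFS date changes.

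Two further inferences are not supported:

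- That every case adds an 8-week interval to DoR and PFS. An unscheduled scan, death or censoring can come first, and if the earlier CR is changed to PR there may be no progression at that visit.
- That the rule produces spurious disagreement with central review. The central reviewers' conventions after a CR may be in the Independent Review Charter, which is not available here.

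**What to change.** Replace Step 4 so that no visit with target disease present stays CR:

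- **All target lesions measured, a non-nodal target lesion above 0 mm after a CR:** assign PD, as in footnote a and Protocol 8.4.1. Alternatively, through a documented data-review step before database lock, change the earlier CR to PR and re-derive both visits from baseline. The review step has to be written down, because investigator visit responses are programmed and neither document describes how such a change would be made.
- **Any target measurement missing and PD not assignable:** assign NE under the existing missing-data rule.
- **A node back at 10 mm or more with a rise below the PD threshold:** flag it for the same review, and state one rule that reconciles footnote a with the Table 3 threshold.

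While editing, use one absolute threshold in Table 3 and in the PFS definition, since at least 5 mm and more than 5 mm differ exactly at the 5 mm default. State also how a rise from 0 mm is handled.

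The cost is a short SAP revision, a small programming change and the review procedure. A few investigator CRs may be lost, and some investigator progression dates may become earlier because of measurement noise.

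### SAP 3.1.1: the rule for more than one third of target lesions treated zeroes the wrong lesions, and two sentences disagree on CR; low impact, investigator-derived responses only

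*SAP*

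**What the plan says.** SAP 3.1.1 gives the rules for target lesions (TLs) that are irradiated, operated on or embolised during the study:

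- **Step 1.** First, "the diameters of the TLs (including the lesions that have had intervention) will be summed" and tested for PD in the ordinary way. A PD found here stands.
- **Steps 2 and 3.** If no more than one third of TLs are treated, the treated ones are dropped, the sum is scaled up, and PD, PR or SD is assigned.
- **More than one third treated.** The response is NE "unless the sum of diameters of TL without intervention would result in PD". A bracket then spells out the test: PD holds if, "if using a value of 0 for non-intervention lesions", "the sum of diameters has still increased by 20% or more compared to nadir" and the rise is at least 5 mm.
- **Nadir.** A separate sentence leaves treated lesions out of the previous minimum sum, with scaling where appropriate. It does not say whether this governs Step 1, the more-than-one-third branch, or both.
- **CR.** Step 3 says "Patients with intervention are evaluable for CR as long as all non-intervened lesions are 0" (nodes below 10 mm) and each treated lesion is recorded as 0. After the scaling example the SAP says "CR will not be allowed as a TL response for visits where there are lesions with intervention" and "Only PR, SD or PD (or NE) could be assigned as the TL visit response in these cases".

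Under SAP 3.1, investigator visit responses are derived by program from these rules. ICR readers supply their own visit responses.

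**The concern.** These sentences are the programming specification for investigator responses, so wording errors can become coding errors. The main clause asks whether the untreated lesions have progressed on their own. The bracket removes exactly those lesions and keeps the treated ones, which the same section expects to shrink. The two CR statements cannot both be coded.

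At stake are investigator-based ORR, BoR, DCR, DoR and PFS, the concordance table between investigator and ICR (SAP 4.2.7.3) and, in principle, the futility count, which uses investigator responses (SAP 5). SAP 3.2.1 does not treat radiotherapy as a subsequent anti-cancer therapy for ORR, so a response recorded after irradiation can count.

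**Working it through.** **1. The SAP's own example.** Nadir: 7.2 + 6.7 + 4.3 + 8.6 + 2.5 = 29.3. Follow-up of the four untreated lesions: 7.1 + 6.4 + 4.0 + 8.5 = 26.0. The same four at nadir: 29.3 − 2.5 = 26.8. Scaled sum: 26.0 / 26.8 × 29.3 = 28.4, as stated. One of five lesions is treated (0.2, below 1/3), so the example never reaches the faulty branch.

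**2. Direction of the bracket.** The main clause keeps untreated lesions; the bracket zeroes them. The missing-TL rule in the same section works the other way: it tests for PD with the lesions that cannot be relied on (those not recorded) taken as gone. The bracket is therefore inverted relative to both its own sentence and the parallel rule.

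**3. When the inversion matters.** Let U and T be the follow-up sums of untreated and treated lesions, and N the nadir. PD requires (S − N)/N ≥ 20% ("percentage changes from baseline and previous minimum should be rounded to 1 d.p") and S − N ≥ 5 mm, with:

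- Step 1: S = U + T
- Main clause: S = U
- Bracket: S = T

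U + T is at least as large as U or T. With the same N throughout, any PD found by the main clause or the bracket has already been found at Step 1. If treated lesions are unmeasured, the missing-TL rule tests U against N and gives the main clause's answer. No response changes.

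The result differs if Step 1 uses the full nadir and the more-than-one-third branch uses a nadir of untreated lesions only. Two hypothetical cases, with lesions 2 and 3 treated (2/3 of TLs):

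| | Missed PD | False PD |
|---|---|---|
| Nadir (mm) | 20/30/30 | 10/30/30 |
| Follow-up (mm) | 30/5/5 | 10/28/28 |
| Step 1, full nadir | 40 v 80: −50%, not PD | 66 v 70: −5.7%, not PD |
| Main clause, untreated nadir | 30 v 20: +50%, +10 mm, **PD** | 10 v 10: 0%, **NE** |
| Bracket, untreated nadir | 5 + 5 = 10 v 20: −50%, **NE** | 28 + 28 = 56 v 10: +460%, +46 mm, **PD** |

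With the full nadir in the branch, main clause and bracket agree on NE in both cases (30 and 10 v 80; 10 and 56 v 70). Rounding plays no part in any of these.

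**4. The CR conflict.** Take a patient with every TL recorded as 0, some of them treated.

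| | Step 3 | Later paragraph |
|---|---|---|
| ≤ 1/3 treated | CR | PR (scaled sum 0, −100%) |
| > 1/3 treated | CR | NE |

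In the first row ORR and DCR do not move. BoR can move from CR to PR, provided non-target disease has also gone or was absent, because SAP Table 5 otherwise makes the visit PR either way. In the second row a responding visit becomes NE, which can change investigator ORR, DCR and DoR. This conflict does not depend on Step 1 or on the nadir.

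**The case against.** A reader might infer that any patient with more than one third of TLs treated and growing untreated lesions is coded NE, delaying investigator PFS. The documents do not support that. Take nadir 20/6/6 mm (sum 32) and follow-up 40/4/4 mm with the two small lesions irradiated. The bracket alone gives 4 + 4 = 8 mm, but Step 1 runs first and gives 48 v 32 mm: +50%, +16 mm, PD. That PD stands. As shown above, this holds generally when one nadir is used throughout.

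There is also support for the full nadir: the missing-TL rule takes the nadir only from assessments with all TLs recorded. But that note concerns missing measurements, and the separate sentence dropping treated lesions from the previous minimum is not limited to any step. The harmful reading therefore stays open, though it is not the only one.

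The reach is narrow. Protocol 7.7 limits on-treatment radiotherapy to painful bony metastases present at baseline, and Appendix F makes bone lesions non-measurable unless they have a measurable soft-tissue component. Treatment of more than one third of TLs should be unusual on study drug. It is not excluded: scanning continues after treatment stops without progression (protocol 4.3.2), and PFS is not censored at later therapy (SAP 3.2.2).

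None of this answers the CR contradiction.

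**Conclusion.** Both defects stand as errors of wording in the current SAP, and nothing elsewhere in the documents resolves them. Their impact is low.

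- The inverted bracket is harmless if Step 1 and the missing-TL rule run first against the full nadir. It gives missed or false PD if the more-than-one-third branch uses a nadir without treated lesions.
- The CR conflict leaves the response undetermined for a patient whose TLs all meet CR criteria with some treated: CR against PR, or CR against NE.
- Only investigator-derived endpoints, their concordance with ICR and, in principle, the futility count are exposed. No actual change to the futility count is shown. A reader might infer that the primary result is at risk; it is not, because ICR visit responses are not derived by this algorithm.

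The documents do not say how many patients will have TL interventions, so no rate can be given. The lesion sizes above are hypothetical and show the mechanism only. The likely number of affected patients is very small.

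**What to change.** Three edits to SAP 3.1.1 before database lock:

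1. In the bracket, assign the value 0 to lesions **with** intervention.
2. State which nadir the more-than-one-third branch uses: full, or excluding treated lesions. Without this the first edit still leaves the PD threshold open (80 or 20 mm as reference in the missed-PD case).
3. Keep one CR rule. One option is to keep the later prohibition and delete the Step 3 sentence, since a lesion removed or irradiated to 0 is not evidence of drug response.

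The cost is a few SAP sentences, with no effect on data collection, sample size or the primary endpoint. The one downside is that, under the prohibition, a rare investigator CR becomes PR or NE.
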